#### **1. Title:**

The use of coronally advanced flap and subepithelial connective tissue graft with or without platelet rich fibrin in the treatment of Miller class I or II gingival recession: a randomized clinical trial.

#### **2. Trial registration:**

NCT03199118

#### **3. Protocol version**

Protocol no 1., revised and approved by the Ethics Committee of Scientific Research - Faculty of Oral and Dental Medicine- Cairo University in **30/09/2017**.

#### **4. Funding:**

Self-funding.

#### **D. Role of steering committee**

- Department of Oral Medicine and Periodontology, Faculty of Oral and Dental Medicine - Cairo University.

It is responsible for ensuring that the research idea follows the research plan of the department .

- Evidence Based Committee, Faculty of Oral and Dental Medicine - Cairo University.

It is responsible for:

- Pico revision.
- Protocol revision.
- Reporting the methodology.
- Sample size calculation and reporting of statistical methods.

- Ethical Committee, Faculty of Oral and Dental Medicine - Cairo University

It is responsible for:

- Ensuring that the trial does not violate privacy, ethical issues, or human rights.
- Supplying the main investigator with a template of informed consent.
- Approving the research, once it fulfills the required ethical criteria.

- Faculty and University board

It approves the protocol once it is approved by the previously mentioned boards and committees.

## **Introduction**

### **6. Background and rationale**

Gingival recession is a frequent, unwanted apical shift of the marginal tissue beyond the cemento-enamel junction (CEJ) and may cause faulty dimensions of keratinized tissue and aesthetic problems. The high concern in aesthetics and the resulting need to solve related problems such as hypersensitivity and root caries have preferred the advancement of many surgical plan that permit the coverage of exposed roots (**Roccuzzo et al., 2002**).

**- Statement of the problem:**

Gingival recession (GR) is a typical appearance in many populaces, and is considered as an early indication of periodontal sickness. A review showed that gingival subsidence is a typical condition with a pervasiveness of 68% for males contrasted with females who had 32% gingival recession (**Manchala et al.2012**).

**- Rationale for carrying out the trial:**

Subepithelial connective tissue graft (SCTG) secured by a coronally advanced flap (CAF) is one of the substantial surgical alternatives and is utilized as often as possible because of its great consistency (**Wennstrom and Zucchelli, 1996; Paolantonio et al., 2002; Tozum and Demiralp, 2003**). However, uncertain complete root coverage (between 18.1 %and 86.7%) has been documented as well as confined regeneration of the lost attachment apparatus with a remedial through long junctional epithelium or adaptation of connective tissue to the root surface after the use of CAF+SCTG (**Cummings et al. 2005**).

One of the enhancers of periodontal tissue regeneration and promoters of early wound healing is found to be the Platelet rich fibrin (PRF) (**Tozüm et al. 2003**). There are only a few reports documenting the use of platelet rich plasma (PRP) in aesthetic periodontal surgery. **Petrungaro (2001)** published a case series in which PRP, SCTG and collagen membranes were used to cover gingival defect. The 2 months study resulted

in 3 mm root coverage. Accordingly, this study will assess the effect of PRF as an adjunct to CAF+SCTG on root coverage outcomes.

## Introduction and review of literature

Gingival recession [GR] has been characterized as an apical move of the gingival edge over the CEJ and the unmasking of the root surface to the oral condition. (**Kassab et al.2003**). It is a familiar and unwanted condition that is commonly seen in dental clinics and affects population of all ages across the planet, represents the status of periodontal tissue and that's why it is not seen as a disease itself. Its existence is annoying for patients due to esthetic, mental and functionnal issues, e.g. dentine hypersensitivity, root caries and abrasion, cervical wear, tooth movement and dental erosion because of the exposure of the root surface to the oral environment (**Tugnait et al.2001**). **Armittage (1999)** has described forms of GR in the absence of periodontal disease which are known as developmental or acquired deformities and conditions.

The etiology of GR is multifactorial and is dependably the aftereffect of more than one component acting together, for example, anatomical [alveolar bone dehiscence, high muscle connection, occlusal injury, frenal pull, thin gingival biotype], inflammatory [destructive periodontal disorder, nearness of dental plaque and supra/subgingival calculus, inadequate teeth brushing], traumatic variables [vigorous oral cleanliness routine, oral piercing] and iatrogenic elements identified with reconstructive, conservative, orthodontic, periodontologic or prosthetic treatment (**Tugnait et al.2001; Kassab et al.2003; Dilsiz et al.2010**).

Normal periodontal tissue can be affected by GR (**Tugnait et al.2001**) and looks like a wedge shaped lesions on the buccal surface of the teeth, notably associated with malposed teeth and hard toothbrush use (**Khocht et al.1993**), while in persons with bad oral hygiene it can be seen on any tooth surface (**Loe et al.1992**). In majority of cases, root coverage methods not just aims to completely cover the denuded root and to enhance esthetics, but also to increase the width of the gingival tissue covering the recessions to enhance long term stability. (**Kennedy et al.1985**).

Free gingival grafts, grafts bringing together two modalities, pedicle grafts and guided tissue regeneration are among several treatment options for covering the exposed roots and to increase the width and thickness of the keratinized gingiva (**Bruno, 1994**). Better esthetics, ease of plaque control and reduction of hypersensitivity are the main outcomes of these procedures. (**Michaelides and Wilson, 1994**).

CAF brought about the re-development of epithelial and connective tissue attachment with insignificant bone repair. Thereafter, many additional agents have been applied to improve healing and additionally reinforce clinical result. These include guided tissue regeneration (GTR) Bio-resorbable membrane (**Zucchelli *et al.*, 1998**), enamel matrix proteins SCTG (**Berlucchi *et al.*, 2002**) recombinant growth factors, PRP and PRF (**Gonshor, 2002**). One of the highly predictable surgical options is the CTG covered by a CAF (**Wennstrom and Zucchelli, 1996; Paolantonio *et al.*, 2002; Tozum and Demiralp, 2003**). However, inconsistent complete root coverage (between 18.1 %and 86.7%) and limited regeneration of the missing attachment apparatus with a healing through long junctional epithelium or adaptation of connective tissue to the root surface after the use of CAF+SCTG (**Cummings *et al.* 2005**).

According to **Marx *et al.* (1998)** who first reported applications and clinical benefits of PRP, it is “a volume of autologous plasma that has a platelet concentration above the baseline”. Due to its good effect on wound healing acceleration, PRP has become a target of lots of researches. It is derived from concentrated platelets, allowing it to deliver a greater concentration of autologous growth factors including platelet derived growth factor, transforming growth factor- $\beta$ , vascular endothelial growth factor, epithelial growth factors, insulin like growth factor. (**Okuda *et al.*, 2003**).

The use of PRF, a second-generation platelet concentrate, gives more advantages than the PRP. The main difference between PRF and commercially available PRP systems is that PRF does not need bovine thrombin or other exogenous activators in the preparation process. A gel-like substance is obtained after PRF preparation, containing high concentrations of non-activated, functional, intact platelets, contained within a fibrin matrix, that release, a relatively constant concentration of growth factors over a period of 7 days. Also a membrane can be produced by squeezing the gel-like matrix that can be

used as fibrin bandage acting as a matrix to fasten the healing of wound edges. Moreover its preparation is relatively easy, simple and fast. An economical autologous membrane is obtained in nearly 1 min and therefore the cost of a membrane and bone graft is avoided (**Thorat et al. 2011**). Homeostasis and wound healing are stimulated by PRF and it has a supportive effect on the immune system, cell migration, and proliferation (**Dohan et al.2006**)

Numerous clinical and histological studies reveal that a specific platelet-concentrated therapeutic concept could be an encouraging medium for the enhancement of soft tissue healing and regeneration in periodontology and implantology (**Pini-Prato et al., 1999**). Promising results have been recorded with the use of PRF in several periodontal surgical techniques, and healing of intrabony and furcation defects (**Sharma et al.2011**). It may be thought that PRF can have a positive effect on the treatment outcomes of root coverage technique.

#### **-Aim of the study**

The aim of this randomized controlled clinical trial with a 6 months follow-up is to evaluate the effectiveness of CAF+SCTG+PRF in the treatment of Miller class I and II recession defects and to compare the outcomes to CAF+SCTG alone.

#### **-PICOTS elements:**

**P (Patient/ Population):** Patients with Miller's class I or II gingival recession.

**I (Intervention):** root coverage using CAF with SCTG and PRF.

**C (Comparator /Control):** root coverage using CAF with SCTG alone.

**O (Outcome):** recession depth

**T:** 6 months follow-up

**S (Study design):** Randomized controlled clinical Trial

**Research question:**

In patients with Miller class I or II gingival recession, does the use platelet rich fibrin in conjunction with CAF and SCTG reduce the recession depth if compared to CAF and SCTG alone?

**7. Objectives of the study:**

This research will be conducted in an attempt to achieve complete root coverage with physiologic probing depth and a harmonious view with the adjacent tissues using PRF in conjunction with CAF and SCTG.

 **Research hypothesis:**

Null hypothesis: In patients with Miller class I and II gingival recession, there is no difference in root coverage outcomes following placement of PRF in conjunction with CAF and SCTG compared to CAF and SCTG alone.

 **The primary objective:**

Recession depth which will be measured before the surgical procedure, then after 3 and 6 months.

 **The secondary objectives:**

	Outcome name	Measuring Device	Measuring Unit
Primary1ry	Recession depth	William's graduated Periodontal probe	mm
Secondary2ry	Recession width	William's graduated Periodontal probe	mm
	Root coverage gain	William's graduated Periodontal probe	mm
	Probing depth	William's graduated Periodontal probe	mm

		probe	
Clinical attachment level	William's graduated Periodontal probe	mm	
Gingival biotype	William's graduated Periodontal probe	mm	
Width of keratinized gingiva	William's graduated Periodontal probe	mm	
Patient satisfaction	Printed questionnaire Binary ( Zuhr et al.2014 )	Yes/No	
Root coverage esthetic score	Score (Cairo et al. 2009)	Categorical	
Post-Operative Pain	Numerical Rating Scale (NRS) (Breivik et al. 2008)	Numerical	

## 8. Trial design:

Parallel groups, Randomized Controlled Clinical Trial

## Methods

### 9. Study setting:

Study is to be conducted in the Oral Medicine and Periodontology department, Faculty of Oral and Dental Medicine – Cairo University, Egypt.

Patients are to be selected from the outpatient clinic of the department of Oral Medicine and Periodontology-Cairo University:

- Dental units: Adec / knight
- Operator: PhD degree student in periodontology department
- Assistant: present

### 10. Eligibility criteria

**i) Inclusion criteria:** Patients eligible for the trial must comply with all of the following:

- 1) Patients 18 years and older
- 2) Buccal recession defects classified as either Miller class I or II gingival recession.
- 3) Clinical indication and/or patient request for recession coverage
- 4) Good oral hygiene

**ii) Exclusion Criteria**

- 1) Miller Class III and IV gingival recession.
- 2) Any systemic diseases or any medication.
- 3) Pregnancy.
- 4) Patients undergoing radiotherapy.
- 5) Handicapped and mentally retarded patients.
- 6) Current and former smokers as smoking is a contra-indication for plastic periodontal surgery (Khuller 2009).
- 7) Teeth with cervical restorations, abrasion.

## **11. Intervention:**

### **11a- General operative procedures:**

#### **Preoperative evaluation**

A periapical radiograph using paralleling technique will be performed for each patient.

The patients will be randomly assigned into two groups;

Group A: patients receiving CAF with SCTG alone.

Group B: patients receiving PRF+CAF+SCTG.

#### **Clinical examination:**

Each patient will be examined intra-orally to check the conformity of the patient to the eligibility criteria mentioned before. If the patient meets the criteria, phase I therapy for

periodontal plastic procedures will be performed including thorough supragingival scaling and subgingival debridement. Maintenance of proper plaque control (both mechanical and chemical) by the patient will be also implemented.

### **Surgical procedures:**

#### **SCTG harvesting:**

A measurement of the approximate length and width of the graft required will be taken. The graft will be harvested from the palate between the distal aspect of the canine and the midpalatal region of the first molar. Two parallel incisions will be performed in the palate using blade n.15, staying at least 2 mm away from the tooth margin. Pressure will be applied to the donor site with gauze soaked in saline after the graft will be taken. Silk sutures are used to simultaneously approximate both the flap margins and the entirely undermined donor area.

#### **Surgical protocol:**

The surgical area will be prepared and adequately anesthetized using 2% lignocaine HCL containing 1:80,000 epinephrine by giving block and infiltration anesthesia. After obtaining adequate anesthesia, two vertically divergent incisions (i.e. one mesial and one distal, immediately adjacent to the defect) extending beyond the MGJ will be made on the buccal aspect of the involved tooth. The sulcular incision will then be placed up to the end of the vertical incisions. Care will be taken to see that the papilla is intact. A trapezoidal flap will be elevated by a sharp dissection with no. 15 scalpel blade to raise a combined full-partial thickness flap to the level of the MGJ.

The flap will be extended well beyond the mucogingival junction so that it exhibits no tension when pulled coronally beyond the CEJ and should be extended at least 5 mm coronal to the most apical margin of the bony dehiscence. The intact papillae mesial and distal to the recession will be de-epithelialized to provide a bleeding connective tissue bed for future the SCTG.

In the test group (group A), the root surface will be covered with the PRF membrane exceeding the margins of surrounding alveolar bone before placing SCTG, while in the control group (group B), SCTG will be placed over the recession defect

leaving the coronal margin of the graft at the level of the CEJ. In both groups, all graft material will be sutured to the periosteum using 5-0 resorbable suture. Finally the flaps will be positioned coronally to the CEJ without tension using 5-0 silk suture. Hemostasis will be achieved by applying gentle finger pressure for 4 minutes.

**PRF preparation:**

This procedure will be done only if the patient is allocated to group A where PRF will be placed and after the flap in the recession site has been prepared. Just before SCTG harvesting, blood will be taken from the anticubital region with a 24-gauge needle and injected into the 10-mL glass coated collection tube without anti-coagulant then immediately centrifuged at 2700 rpm for 12 minutes with a table centrifuge. The fibrin clot will be collected from the middle part of the tube and packed tightly in 2 sterile saline impregnated gauze in order to obtain a fibrin membrane.

A post-surgery protocol will be implemented emphasizing wound stability and infection control, including 0.12% chlorhexidine rinse twice per day. Gingival sutures will be removed 2 weeks post-surgery. Mechanical plaque control in the surgical area will be reinstated at week 8 following surgery. Patients will be recalled for supragingival scaling and oral hygiene instructions on a monthly basis for the 6-month observation interval.

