#### **11-d: Concomitant care**

The patients will receive postoperative instructions and oral hygiene guidelines that should be followed during the 6 month follow-up period. Patients will be recalled every 1 week for first month and then every month for supportive periodontal therapy till 6 months follow up.

Medications: Chlorohexidine 0.12% mouthwash 2 times/day for 1 week

Brofen 400 mg 3 times/day for 5 days

Soft tooth brush is to be used

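### Do the post-operative rinse and brushing instructions conflict and leave the grafted site without plaque control until week 8?

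*Combined protocol and SAP*

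**What the plan says.** Two places in section 11 of the protocol describe aftercare.

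- **The closing paragraph under PRF preparation:** "A post-surgery protocol will be implemented emphasizing wound stability and infection control, including 0.12% chlorhexidine rinse twice per day". It gives a frequency and no duration. Sutures come out at 2 weeks. Then: "Mechanical plaque control in the surgical area will be reinstated at week 8 following surgery". The next sentence adds: "Patients will be recalled for supragingival scaling and oral hygiene instructions on a monthly basis for the 6-month observation interval".
- **Section 11-d, Concomitant care:** "Chlorohexidine 0.12% mouthwash 2 times/day for 1 week" and "Soft tooth brush is to be used". The brush line gives no start date and no site. The same section says "The patients will receive postoperative instructions and oral hygiene guidelines that should be followed during the 6 month follow-up period" and "Patients will be recalled every 1 week for first month and then every month for supportive periodontal therapy till 6 months follow up".

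Section 11-c adds weekly follow-up in the first month and a check on hygiene adherence, made by showing patients the plaque picked up on the probe.

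**The concern.** Each section taken alone could produce a different instruction sheet. One has an open-ended rinse and no mechanical cleaning of the operated area until week 8. The other has a one-week rinse and a soft brush with no stated exception for that area. Taken together, the rinse stops at week 1 and cleaning of the site resumes at week 8, which seems to leave a long interval with nothing specified, in a protocol that says it emphasises infection control.

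The protocol's own background lists plaque and poor brushing among the causes of recession, and recession depth is the primary outcome. If patients received different regimens, the outcome could become more variable. If the unblinded operator applied them differently by arm, the comparison could be biased. All 34 planned patients (17 per group, section 14) would be exposed to the ambiguity.

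**Working it through.** The plan states no figure for this point, so the check is date arithmetic and a side-by-side reading.

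**Length of the interval**

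Inputs: end of rinse at week 1 (section 11-d); restart of mechanical cleaning at the site at week 8 (PRF preparation).

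- If week 8 means 8 full weeks after surgery: 8 − 1 = 7 weeks = 49 days, and 49/56 = 88% of the period without mechanical cleaning.
- If week 8 means the start of the eighth week: 7 − 1 = 6 weeks = 42 days.

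Both results require the one-week limit to govern. If the open-ended wording governs instead, the rinse has no stated end and no such interval is established.

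**What else is stated inside the interval**

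One month is 365.25 / 12 / 7 = 4.3 weeks, so monthly recalls fall at about weeks 4.3 and 8.7. One monthly scaling visit therefore lies inside the interval, as do the remaining weekly recalls of the first month. The hygiene guidelines run for the whole 6 months. What is unspecified is daily home care at the operated site, which is narrower than having no plaque control at all.

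**Do the instructions contradict each other?**

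| Item | PRF preparation | Section 11-d | Can both be followed? |
|---|---|---|---|
| Rinse | 0.12%, twice daily, no duration | 0.12%, twice daily, 1 week | Yes: same agent, strength and frequency; one adds a duration |
| Brushing | None in the operated area until week 8 | Soft brush, no site or start given | Yes: the brush line can refer to the rest of the mouth, or to the site after week 8 |
| Recall | Monthly for 6 months | Weekly for a month, then monthly | Yes |

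The two complaints also need opposite premises. The 7-week interval requires the sections to be read as one regimen. The charge that patients may get different regimens requires them to be read separately, and then the interval is not established.

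**Consequence for the comparison**

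If a common aftercare regimen shifts mean recession depth by the same amount c in each arm, the contrast is (mean with PRF + c) − (mean without PRF + c), and c cancels. Bias would need aftercare to differ by arm, or the same aftercare to act differently in the two arms; the documents state neither. Inconsistent advice unrelated to arm would add variance to the 0.38 mm SD used in section 14, but the documents give no figure from which to size that addition.

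**The case for a change.** The strongest opposing argument is that the recalls do not settle the matter. Supragingival scaling is itself mechanical plaque control. If the month-1 scaling includes the grafted site, it sits awkwardly with the week-8 sentence; if it leaves the site out, the interval in site care remains. The adherence check in section 11-c likewise does not say whether the operated tooth is included. This stands: the scope of scaling and plaque checks before week 8 is unclear.

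A second argument concerns layout. The week-8 rule appears under PRF preparation, whose opening sentence limits that procedure to the PRF group. A literal reader could apply the aftercare paragraph to one arm only, and the operator knows the allocation. This carries little weight. The same paragraph covers suture removal and the 6-month recalls, while the surgical protocol sutures both groups and both are followed for 6 months, so the paragraph reads as general aftercare. Section 11-d addresses patients without distinguishing arms, and section 17 keeps the outcome assessor blinded.

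A third argument is that clarifying the text costs only wording. That is true, but a low cost does not show that the plan is defective. Whether a one-week rinse followed by a pause in brushing is adequate is a clinical question for the investigators, and this review takes no position on it.

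**Conclusion.** The concern does not call for a change to the plan. The lines are ambiguous and are not strictly contradictory. The ambiguity amounts to about 6 to 7 weeks without specified daily home care at the operated site, conditional on the one-week rinse limit governing. Weekly and monthly recalls, one monthly scaling visit and the hygiene guidelines fall within that time.

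This is missing detail of a kind the investigators can fill when they write the patient instructions. The rinse duration, the scope of the soft-brush line and the handling of scaling before week 8 have to be read as one regimen, with the content left to them. The conclusion rests on both arms receiving the same aftercare, which is the natural reading of section 11 and is contradicted nowhere. On that basis, following the plan as written does not make the between-group comparison of recession depth wrong. The 88% figure describes days on a calendar and says nothing about bias or power.
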